### **Primary Outcome 1: The change in documented hemoglobin prior to an intraoperative transfusion.**

The hemoglobin of interest for this outcome is the pre-transfusion hemoglobin. See additional definitions above. Additionally, for this primary outcome we will perform a sensitivity analysis, following the same statistical methodology, to compare the effect of including only the first transfusion of the case in those cases with multiple transfusion with our definition.

First, the trend of median pre-transfusion hemoglobin measurement by quarter will be assessed for any change over time by testing whether the slope is significantly different from 0 using a bivariate linear regression model with the dependent variable of median pre-transfusion hemoglobin measurement. If the slope is not significantly different from 0, then the analyses for this aim will conclude. Otherwise, a Joinpoint analysis will be conducted to determine if there are any inflection points in the trend. If no inflection points are found and the slope is negative and significantly different from 0, then Hypothesis 1 will be assumed true. If the Joinpoint analysis finds one or more inflection points in the data, then a Student's t test or Mann-Whitney U test will be used to compare the values between consecutive quarters to analyze the significance of the change. A similar analysis will be conducted at the institution level.

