We hypothesized that: 1) We would observe a reduction in pre-transfusion intraoperative hemoglobin, as a proxy for transfusion trigger, and reduction in nadir hemoglobin in cases where intraoperative transfusion was not performed. 2) A diminishing number of intraoperative transfusions would be observed, overall and at each hemoglobin value. 3) There would be a reduction in the nadir postoperative hemoglobin. 4) That any observed trends would be modulated by year, surgery type, institution and the presence of coronary artery disease. 5) That in the presence of a change in transfusion practice, we would not observe a change in mortality, post-operative myocardial injury or acute kidney injury.

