The primary outcomes of this study are: the change in the pre-transfusion hemoglobin (ie transfusion threshold) and the nadir hemoglobin not-followed with an intraoperative transfusion over the course of the study period. The secondary outcomes of this study are: proportions of cases receiving a packed red blood cell transfusion throughout the study period (including stratification by prior laboratory measurements); the number of units of packed red blood cells transfused during the intraoperative period; the nadir postoperative hemoglobin (lowest value measured 0 – 72 hrs after the completion of intraoperative anesthesia care), the relationship between patient, surgical and institutional factors and the occurrence of transfusion and determination of the subsequent impact of any transfusion trends on blood product utilization; the relationship between in hospital mortality, post-operative myocardial injury, acute kidney injury and the pre-transfusion hemoglobin (for transfused cases – definition below) and lowest (for non-transfused cases) intraoperative hemoglobin.

In this study, we define coronary artery disease based on the present of a discharge ICD9/10 as listed in Appendix 3. Determination of AKI was based on the KIDIGO laboratory based definition AKI (Cr rise of 0.3 mg/dL rise within 48hrs of anesthesia end time or rise by more than 50% in 7 days). We will use intraoperative hemoglobin values documented, regardless of method of measurement. We preferentially use hemoglobin measures over hematocrit if these are documented simultaneously. If only a hematocrit is present at the time of lab measurement, we will perform an estimated conversion to hemoglobin, by dividing by 3. For blood transfusions documented exclusively in volume based units, we will convert this to units by assuming that any blood volume transfused greater than or equal to 250ml and less than or equal to 450 ml in one charting increment corresponds to one unit of blood.

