**Secondary Outcome 2: The number of units of packed red blood cells transfused during the intraoperative period.**

The number of units of pRBC transfused during the intraoperative period will be analyzed similar to Primary Outcome 1.

To determine independent predictors of the number of units of pRBC transfused during a case, two mixed effects linear regression models will be constructed with the independent covariates listed in the methods and the dependent variable of number of units of packed red blood cells transfused. The first model will contain the mixed effect of institution, and the second model will contain the hierarchical mixed effects of primary attending nested within institution.

**Secondary Outcome 3: The nadir postoperative hemoglobin (lowest value measured 0 – 72 hrs after the completion of intraoperative anesthesia care)**

The lowest postop hemoglobin will be examined for a trend over time for all cases using a Joinpoint analysis as for previous outcomes. The lowest postop hemoglobin will be compared at each time point between those with and without an intraoperative transfusion using a Student's t test or Mann-Whitney U test, as appropriate.

**Secondary Outcome 4: The relationship between patient, surgical and institutional factors and the occurrence of transfusion and determination of the subsequent impact of any transfusion trends on blood product utilization.**

Two mixed-effects logistic regression models will be used to determine if surgery type, year, and cardiac disease are independent predictors of intraoperative transfusion. The outcome of intraoperative transfusion will be defined as any PRBC use between Anesthesia Start and

Anesthesia End. The first model will contain the mixed effect of institution, and the second model will contain the hierarchical mixed effects of primary attending nested within institution. Independent variables to be included in the model are: Age, Sex, Elixhauser co-morbidities (as numeric and also CAD y/n, heart failure y/n, cancer y/n), WHO BMI classifications, ASA Status, Pre-op Hb, lowest Intra-op Hb for cases without intraop transfusion or the pre-transfusion hemoglobin, Pre-op Plts (abnormal y/n), Pre-op Creatinine (abnormal y/n), Abnormal coags (y/n – PT, PTT or INR), Surgical Specialty, EBL, Cell saver (Scavenged) blood use (y/n), Emergent Surgery, Use of anti-fibrinolytics (Aminocaproic Acid, Tranexamic Acid, Aprotinin) – y/n, and surgical Case Duration.

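### Primary Outcome 1 reads the median hemoglobin of transfused cases as the transfusion threshold, but the practice under study selects that group, so a real fall in threshold can be understated by an unknown amount

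*Protocol*

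**What the plan says.** The Introduction states Hypothesis 1 as "a reduction in pre-transfusion intraoperative hemoglobin, as a proxy for transfusion trigger", together with a lower nadir in untransfused cases. The Methods name the first primary outcome as "the change in the pre-transfusion hemoglobin (ie transfusion threshold", so the outcome and the threshold are treated as one quantity.

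The section on Primary Outcome 1 regresses the quarterly median on time, with no covariate other than time: "First, the trend of median pre-transfusion hemoglobin measurement by quarter will be assessed for any change over time". Two branches follow:

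- Null slope: "If the slope is not significantly different from 0, then the analyses for this aim will conclude".
- Falling slope: "If no inflection points are found and the slope is negative and significantly different from 0, then Hypothesis 1 will be assumed true".

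The one sensitivity analysis in that section changes only which transfusion of a case supplies the value. Blood loss appears elsewhere, in the covariate list of Secondary Outcome 4: "Surgical Specialty, EBL, Cell saver (Scavenged) blood use (y/n), Emergent Surgery".

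**The concern.** A threshold is a property of the decision: the hemoglobin below which a clinician transfuses. The median among transfused cases also depends on who is transfused. Some patients are transfused because they are bleeding, whatever the last laboratory value, and a tighter threshold need not remove those cases. The protocol itself expects the transfused group to shrink: "A diminishing number of intraoperative transfusions would be observed, overall and at each hemoglobin value". If the shrinkage falls mainly on transfusions prompted by a low value, the mix shifts as a result of the very change being studied.

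The exclusion above 3 units does not settle this, because bleeding cases given 1 to 3 units remain. The 30-minute (or 45-minute) laboratory window fixes timing, not indication. Adjusting for specialty or site would not remove a shift caused by the practice change.

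At stake is the reading of a primary outcome. A null slope could mean an unchanged threshold or a fall hidden by case mix, and the rule ends the aim at that point. A significant fall could understate the change.

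**Working it through.** **The plan's own figure.** The Sample Size section gives about 113,000 cases and a statement that power is sufficient, with no effect size, SD or power value. There is nothing to reproduce, and the question is what the median measures rather than power. The period from January 1, 2012 to July 1, 2017 is 5.5 × 4 = 22 quarters.

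**Assumptions.** The documents give no share or hemoglobin for bleeding-driven transfusions, so every distribution below is assumed. Each model mixes low-value transfusions, which depend on the threshold T, with bleeding-driven ones, which do not. The test is the ordinary regression slope of 22 quarterly medians, two-sided 5%.

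**Model A.** Hemoglobin at decision is N(10, 1.6). The probability of a low-value transfusion is 1/(1 + exp((Hb − T)/0.4)), with T falling from 9 to 8 g/dL. Bleeding-driven transfusions are constant in number with SD 1.5. About 360 cases are transfused per quarter at the start; 1,500 runs per scenario.

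Integrating the curve over the hemoglobin distribution, the low-value transfusion rate is 0.284 at T = 9 and 0.127 at T = 8, a fall of 1 − 0.127/0.284 = 55%. With a starting bleeding share of 40%, bleeding-driven transfusions equal (0.4/0.6) × 0.284 = 0.189. The final share is 0.189/(0.189 + 0.127) = 60%. A starting share of 50% becomes 0.284/(0.284 + 0.127) = 69%.

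| Starting bleeding share | Fitted change in median, bleeding Hb mean 9.3 to 9.8 (g/dL) | Significant fall |
|---|---|---|
| 0% | -0.68 | 100% |
| 20% | -0.44 to -0.41 | 100% |
| 30% | -0.31 to -0.24 | not tabulated |
| 40% | -0.18 to -0.04 | 73% to 9% |
| 50% | -0.07 to +0.13 | 15% to 0% |

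At 50% and mean 9.8 a significant rise occurs in about 30% of runs. With bleeding hemoglobin mean 8.5, the change is -0.51 at a 20% share and -0.27 at 50%, and the fall is detected in at least 97% of runs.

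**Model B, different inputs.** Nadir of other cases N(10.5, 1.7); threshold SD 0.5 between decisions, falling from 8.5 to 7.5 g/dL; 113,000 cases; 60 runs per scenario. The low-value transfusion rate is Φ((T − 10.5)/√(1.7² + 0.5²)): Φ(−2/1.772) = 0.130 at the start and Φ(−3/1.772) = 0.045 at the end. If bleeding-driven transfusions make up a fraction b of all cases, their share of transfusions is b/(b + (1 − b) × rate).

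- b = 0: the median falls 0.80; detected in 100% of runs.
- b = 3%, Hb 9.5: share 19% to 41%; median 8.10 to 7.63.
- b = 5%, Hb 10.5: share 29% to 54%; median 8.28 to 8.44; slope not significant in 95% of runs.
- b = 8%, Hb 9.5: share 40% to 66%; median 8.32 to 8.47; no run with a significant fall, 38% with a significant rise.
- b = 2% to 12%, Hb 8.5: the median falls by 0.63 to 0.18; detected in 98-100% of runs.

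**Relaxing the constant number.** In Model A at 40-50% share and mean 9.3 to 9.8, let bleeding-driven transfusions decline too. With a 25% decline the median changes by -0.32 to -0.07; with 40%, by -0.42 to -0.25; with 55%, equal to the low-value decline, by -0.55 to -0.45. The rise disappears in each case.

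**The case against.** The strongest reply is that a flat or rising median needs inputs found nowhere in the protocol: a large bleeding-driven share, a hemoglobin well above the threshold, and a number that does not decline. Hypothesis 2 expects fewer transfusions at every hemoglobin value, and cell saver and antifibrinolytic use, both recorded, could change over time. The only comparable figure, the European pre-transfusion hemoglobin of 8.1 g/dL cited in the Introduction, lies below the 8.88 g/dL at which the 50%, mean 9.8 scenario starts. That is another population and only a plausibility check. All of this stands: reversal is conditional, and attenuation is the general result.

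The protocol also has analyses that bear on the threshold: Primary Outcome 2; the proportion transfused at each hemoglobin level, 2012 against 2016 (Secondary Outcome 1); and a model of intraoperative hemoglobin under Secondary Outcome 4 which, on the natural reading of its reference to the list above it, adjusts for EBL. In Model B the proportion transfused fell by 7 to 8 percentage points and the untransfused nadir by 0.18 g/dL in every scenario. These are real safeguards, and the null rule does not cancel them. None of them enters the decision rule of Primary Outcome 1, and the protocol does not say how to reconcile them with it.

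A reader might infer that a rising median would count as evidence against Hypothesis 1. The protocol has no such rule; it states only when the hypothesis is taken as true. That the study is labelled descriptive and calls the value a proxy softens the point but does not remove it, because the same text then declares the hypothesis true from this slope.

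**Conclusion.** The point holds as a limit on interpretation. The median among transfused cases is not the threshold, and its trend is biased toward no change whenever bleeding-driven transfusions decline less than low-value ones and sit at a higher hemoglobin. Attenuation appeared at every non-zero share tested with a constant number of bleeding-driven transfusions, including those at mean hemoglobin 8.5. Its size in this study cannot be derived from the documents.

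A reader might conclude that the primary analysis will miss or reverse a real fall. The documents do not support that. It needs roughly 30-50% of transfusions to be bleeding-driven at the start, at a clearly higher hemoglobin and in a roughly constant number. At a 20% share, or with mean hemoglobin 8.5, the test still finds the fall. What the protocol should not do is close the aim on a null slope, or settle Hypothesis 1 from this median alone.

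**What to change.** In the section on Primary Outcome 1:

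1. Delete the rule that ends the analyses for this aim when the all-case slope is not significant.
2. Add a sensitivity analysis that repeats the slope and Joinpoint analysis within EBL strata, with the cut fixed before data extraction. Report by quarter the number of transfused cases and the share above the cut.
3. Do not declare Hypothesis 1 supported or unsupported from the all-case median alone. Read it with the EBL-stratified result, Primary Outcome 2, the proportion transfused at each hemoglobin level, and the EBL-adjusted model under Secondary Outcome 4.

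The cost is protocol wording and one stratified run on a variable already planned. EBL is charted imprecisely, so the strata separate the indications only in part, and each has fewer cases. If a low-EBL stratum kept one fifth of the bleeding-driven cases, which is an assumption, the Model A change there would be -0.63 to -0.46 g/dL for starting shares of 20% to 50%; poorer separation would gain less. For that reason the stratum should support the reading of Hypothesis 1, not replace the all-case result.

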**Primary Outcome 2: The change in documented nadir hemoglobin not followed with an intraoperative transfusion.**

The hemoglobin of interest for this outcome is the lowest documented intraoperative hemoglobin for the case, for those who did not receive an intraoperative transfusion.

The analysis for this outcome will be conducted identical to that for Primary Outcome 1.

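### The primary-outcome rule runs Joinpoint only after a significant straight-line slope, and once a bend is found it falls back on consecutive-quarter tests that do not measure the trend

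*Protocol*

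**What the plan says.** Protocol, Primary Outcome 1, begins by "testing whether the slope is significantly different from 0 using a bivariate linear regression model", with the quarterly median pre-transfusion hemoglobin as the response. Three branches follow.

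- **Slope not significant:** "If the slope is not significantly different from 0, then the analyses for this aim will conclude". Joinpoint is not run.
- **Slope significant:** "Otherwise, a Joinpoint analysis will be conducted to determine if there are any inflection points in the trend". If there are none, the protocol states: "If no inflection points are found and the slope is negative and significantly different from 0, then Hypothesis 1 will be assumed true".
- **Slope significant and one or more inflection points:** a Student's t or Mann-Whitney U test "will be used to compare the values between consecutive quarters to analyze the significance of the change". Nothing says how these results bear on Hypothesis 1.

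The statistical row of the summary table on the first page also makes Joinpoint conditional on a non-zero slope. For Primary Outcome 2: "The analysis for this outcome will be conducted identical to that for Primary Outcome 1". Secondary Outcomes 1 and 2 use a similar analysis, and Primary Outcome 1 and Secondary Outcome 1 repeat it by institution. Hypothesis 1 in the Introduction has two components: "We would observe a reduction in pre-transfusion intraoperative hemoglobin, as a proxy for transfusion trigger, and reduction in nadir hemoglobin in cases" without transfusion.

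**The concern.** Joinpoint exists to locate changes in the direction or steepness of a trend. Making it depend on a significant single line means it is skipped when a reversal has flattened that line. The section sets out to assess any change over time, so a non-monotone change is within its scope.

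The second problem lies further down. When Joinpoint does find structure, the plan leaves the trend model and compares neighbouring three-month blocks. A change in practice that takes years is then examined in steps of one quarter. The result can be a list of mostly non-significant comparisons with a few chance findings, and the protocol gives no way to read that list as support for or against Hypothesis 1. Because the rule is reused, the problem extends to both primary outcomes and at least two secondary ones.

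**Working it through.** The Sample Size section gives a database count (around 113,000 cases) and no power calculation, so there is no planned figure to reproduce. The decision rule itself was checked.

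**Inputs from the protocol.** 1 January 2012 to 1 July 2017 is 22 quarters, hence 21 adjacent pairs. 113,000 / 22 ≈ 5,136 cases per quarter.

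**Assumptions (not in the protocol).** Two-sided alpha 0.05; 5%, 10% or 20% of cases transfused (257, 514 or 1,027 per quarter); SD of pre-transfusion hemoglobin 1.2 or 1.5 g/dL. With SE(median) = 1.2533 × SD / √n, these give a quarterly noise SD of about 0.05 to 0.12 g/dL. The simulations use 0.06 to 0.15. A one-joinpoint search with a simulated 5% critical value stands in for Joinpoint.

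**1. The gate.** The slope is b = Σ(t − t̄)y / Σ(t − t̄)², with Σ(t − t̄)² = 22 × (22² − 1) / 12 = 885.5. If the means are symmetric about the middle of the period, the numerator cancels and the expected slope is 0, whatever the depth of the dip or the sample size. The misfit also inflates the residual variance, so the test rejects even less often than 5%.

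| Dip (g/dL) | Noise SD | Slope significant | Ungated joinpoint test |
|---|---|---|---|
| 0.3 | 0.10 | 0.8% | about 94% |
| 0.3 | 0.15 | about 2% | 63–65% |
| 0.5 | 0.10 | under 0.1% | about 100% |
| 0.5 | 0.15 | about 0.6% | about 98% |

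Partial recovery matters less. Over falls of 0.3 to 1.0 g/dL, the gate opens in 0–10% of runs with 75% recovery and in 34–100% with 50% recovery.

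**2. Steady decline.** For a total fall of 0.42 g/dL the slope is 0.42 / 21 = 0.02 per quarter, with SE = noise SD / √885.5 = 0.0034 to 0.0050 for noise SD 0.10 to 0.15. The slope is significant in about 96–100% of runs, and a false joinpoint appears in roughly 5%. The no-inflection branch handles this case properly.

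**3. Fall then plateau.** For 0.5 g/dL over 11 quarters and then flat, the slope is significant in 99–100% of runs. A joinpoint is found in about 45–100% (noise SD 0.15 down to 0.06). Those series go to the consecutive-quarter tests.

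**4. Power of those tests.** I take them as comparisons of patient-level values. The step is 0.5 / 11 = 0.045 g/dL, and SE = SD × √(2/n).

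- n = 257, SD 1.5: SE = 0.132, ratio 0.34, power about 6%.
- n = 1,027, SD 1.2: SE = 0.053, ratio 0.86, power about 14%.
- Comparing the start with the end of the same fall: 96–100%.
- Primary Outcome 2 (assumed 4,100–4,900 cases per quarter, SD 1.5–2.0): 18–32% per pair.

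**5. Chance findings.** With no change at all and all 21 pairs tested unadjusted, independence would give 1 − 0.95²¹ = 66% for at least one significant result. Allowing for the quarter that adjacent pairs share, simulation gives about 60%.

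**The case against.** The strongest reply has four parts.

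**The rule does confirm a gradual decline.** A reader might infer that the plan cannot confirm gradual change at all. The protocol does not support that: a steady fall without inflection is accepted on the slope alone, and usually would be. The low power applies only after an inflection is found. This stands in full.

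**A full fall and recovery is not a reduction.** Hypothesis 1 predicts a fall, and a complete V has no net fall, so the verdict on Hypothesis 1 would be the same under the rule proposed below. The background also gives no reason to expect complete reversal. This stands too. What the gate loses in that case is the finding that practice changed and changed back.

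**Other analyses are not gated.** The regression models carry time as a fixed effect, Secondary Outcome 1 compares 2012 with 2016 by hemoglobin level, and Secondary Outcome 4 models intraoperative hemoglobin. A change would therefore not go wholly unseen. These analyses are secondary, however, and do not repair the primary rule.

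**The number of pairs and the alpha are not stated.** That is correct, and multiplicity may be handled in an analysis plan not shown. The 60% figure is therefore conditional. The choice of test is fixed in the protocol.

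A reader might also infer that Hypothesis 1 is declared true from Primary Outcome 1 alone. Since Primary Outcome 2 repeats the identical analysis, the rule can be read component by component. Whether both are needed is simply not said.

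**Conclusion.** The point holds in two places. First, the slope gate stops the analysis on a near-complete fall and recovery. For a symmetric V this follows from the algebra and needs no assumption about SD or sample size; the simulated percentages do depend on the assumed noise. Second, in the inflection branch the planned tests do not estimate the trend, have little power per pair for Primary Outcome 1 (somewhat more for Primary Outcome 2), and have no stated link to Hypothesis 1. The missing link is a matter of the text alone; the power figures rest on the assumed SD, transfusion share and size of fall.

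The no-inflection branch is sound. Because the defect is in the decision rule for both primary outcomes, and following it can end in no reported change or in uninformative pairwise results when practice did change, it should be corrected even though the study is descriptive.

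**What to change.** 1. Remove the slope condition. Run Joinpoint (or a segmented regression) for every series, and let its own test decide the number of segments. Amend the summary table to match.
2. Replace the consecutive-quarter tests with the slope of each segment and the average quarterly change over the whole period, each with a 95% CI.
3. In every branch, call a component of Hypothesis 1 supported if the upper 95% limit of its whole-period average change is below 0. With no joinpoint this average is the single slope, so the present confirming branch is kept in substance.
4. State whether Hypothesis 1 as a whole needs both components.
5. Carry the same wording to Primary Outcome 2, Secondary Outcomes 1 and 2, and the institution-level analyses.

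The cost is protocol wording and slightly more analysis, with the same data and software.

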### **Statistical Analysis:**

Summary statistics will be presented as means and standard deviations or medians with interquartile ranges for continuous variables, as appropriate, and frequencies with percentages for categorical variables. All continuous variables will be assessed for normality using the Kolmogorov-Smirnov test. Univariate demographic and covariate comparisons between those who did and did not receive a transfusion will be analyzed using Student’s t-tests or Mann-

Whitney U tests for continuous variables, and Chi-squared or Fisher's Exact tests for categorical variables, as appropriate.

Mixed-effects multivariable linear or logistic regression models will be constructed as necessary. Prior to model entry, all covariates selected for model inclusion will be checked for collinearity using a Pearson correlation matrix. Variable pairs with a correlation  $> 0.70$  will be considered collinear and either combined into one variable, or one of the covariates will be excluded from the model. All variable pairs with a correlation  $\leq 0.70$  will be deemed fit for model entry. Model effect size will be presented as adjusted odds ratios with 95% confidence intervals, or beta coefficients with standard error, as appropriate. The covariates to be included in all models (discussed below) are surgical specialty, age, BMI, sex, presence of coronary artery disease, Elixhauser comorbidities, quarter of the study period, and hemoglobin. Time will be included in all models as a fixed effect by quarter, half-year, or year based on available sample size. The first quarter, half-year, or year will serve as the reference group. The random effects of institution and attending, where appropriate, will be presented as intraclass correlation coefficients and median odds ratios with 95% confidence intervals. Measures of effect size will be reported as adjusted odds ratios for logistic regression and beta coefficients for linear regression, and will be presented with 95% confidence intervals. For logistic regression models, model predictive capability will be presented as the area under the receiver operating curve (ROC) c-statistic. For linear regression, the extent to which the model explains the variability of the data will be presented as  $R^2$  values. Covariates with a statistically significant adjusted odds ratio or beta coefficient (as appropriate) will be considered independent predictors of the outcome.

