To determine if transfusion practice changed over time, a multivariable linear regression model will be constructed as above, with the outcome of intraoperative hemoglobin (lowest throughout the case for those who were not transfused and prior to transfusion as defined above for those who received an intraop transfusion). The covariate of intraoperative transfusion y/n will be added to the list specified above. Model-based least square means with standard error will be reported and compared between those who were transfused and those who were not with a Student's t test. These means are the adjusted marginal mean of the outcome for the population, which we will consider a proxy for transfusion threshold. A one-way t-test will be used to test if the model-based mean hemoglobin for those who were transfused changed over time.

An observed vs. expected analysis will be conducted for the occurrence of transfusion, comparing practice patterns between the first and last time periods (quarters/half-years/years as appropriate) using a Chi-squared or Fisher's Exact test.

**Secondary Outcome 5: The relationship between in hospital mortality, post-operative myocardial injury, acute kidney injury and intraoperative hemoglobin concentration (with and without transfusion).**

Due to the small sample size expected for in-hospital mortality and post-operative myocardial infarction, the outcome for this analysis will be a composite variable of post-operative morbidity and mortality. Multiple mixed-effects logistic regression models will be used to determine if perioperative hemoglobin is an independent predictor of post-operative morbidity and mortality in ranges which are typically considered consistent with restrictive transfusion. In one model the lowest intraoperative hemoglobin will be considered as a continuous variable, for modelling outcome, in another, we will compare lowest intraoperative hemoglobin ranges of <6 g/dL, 6-7 g/dL, 7-8 g/dL, 8-9 g/dL, 9-10 g/dL, > 10 g/dL. Due to sample size constraints, we may have to redefine these boundaries. We will further analyze this to include the mixed effect of institution, and the second model will contain the hierarchical mixed effects of primary attending nested within institution. All models will include transfusion as a binary variable.

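### Both primary outcomes are decided on the slope of a crude all-site quarterly median, so a shift in site or specialty mix can create or mask a trend

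*Protocol*

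**What the plan says.** For Primary Outcome 1, "the trend of median pre-transfusion hemoglobin measurement by quarter will be assessed for any change over time", "using a bivariate linear regression model with the dependent variable of median pre-transfusion hemoglobin measurement". Quarter is the only regressor. Two consequences follow from that one slope. If it is null: "If the slope is not significantly different from 0, then the analyses for this aim will conclude". If it is significant, a Joinpoint analysis follows, and then: "If no inflection points are found and the slope is negative and significantly different from 0, then Hypothesis 1 will be assumed true". The section on Primary Outcome 2 applies the identical procedure to nadir hemoglobin in non-transfused cases, and the synopsis repeats the bivariate test.

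Two related analyses are planned. The Primary Outcome 1 section closes with "A similar analysis will be conducted at the institution level". Under Secondary Outcome 4 there is an adjusted model: "To determine if transfusion practice changed over time, a multivariable linear regression model will be constructed as above". Neither is mentioned in the decision rule, and nothing says what follows if they disagree with the pooled slope.

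The Introduction states as Hypothesis 4: "That any observed trends would be modulated by year, surgery type, institution and the presence of coronary artery disease". It also reads pre-transfusion hemoglobin as a stand-in for the transfusion trigger, so Hypothesis 1 is a statement about practice.

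**The concern.** A pooled quarterly median mixes two things: how each site and specialty transfuses, and how much each contributes to that quarter's cases. The protocol anticipates 8 sites and lists 10 specialties, and it names institution and surgery type as factors of interest in Aim 2. If groups differ in their usual pre-transfusion hemoglobin and their shares drift, the pooled median moves even when every group's median stays put. An opposing drift can cancel a real fall, and the null-slope gate would then close the aim.

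The Statistical Analysis section says "The covariates to be included in all models (discussed below) are surgical specialty, age, BMI, sex, presence of coronary artery disease, Elixhauser comorbidities", and it provides for institution as a random effect. A bivariate regression on 22 medians can carry none of these terms. The primary verdict is therefore reached without the adjustment that the protocol otherwise treats as standard.

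**Working it through.** **Inputs from the protocol.** The period 1 January 2012 to 1 July 2017 gives 22 quarters. About 113,000 cases have an intraoperative value, so 113,000 / 22 = about 5,136 per quarter. The protocol gives no power, effect size, SD or alpha for this test, so there is no figure of its own to reproduce.

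**Assumptions (not in the documents).** Two groups of cases with fixed medians and within-group SD 1.2 g/dL; the lower group's share moves linearly from 45% to 55% or from 40% to 60%; two-sided 5% test; 200 or 400 usable transfused cases per quarter (3.9% or 7.8% of 5,136).

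**Step 1: movement of the pooled median.** With lower-group share p and group medians a and b, the pooled median m solves p·Φ((m − a)/1.2) + (1 − p)·Φ((m − b)/1.2) = 0.5. For a = 8.0 and b = 9.0, m is 8.606 at p = 0.40 and 8.394 at p = 0.60, a fall of 0.21 g/dL.

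**Step 2: chance of a significant negative slope.** SE of a quarterly median = 1.253 × 1.25 / √n, which is 0.111 (n = 200) or 0.078 (n = 400). The sum of squares of time is 22 × (22² − 1) / 12 = 885.5. The slope SE is therefore 0.111 / √885.5 = 0.00372 (n = 200) or 0.00263 (n = 400). A fall d over 21 steps has noncentrality (d / 21) / slope SE. For d = 0.211 and n = 200 this is 0.01005 / 0.00372 = 2.7. The chance that t on 20 df exceeds 2.086 is then 73%.

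| Group medians | Share shift | Fall (g/dL) | n = 200 | n = 400 |
|---|---|---|---|---|
| 8.2 / 8.8 | 10 points | 0.06 | 11% | 18% |
| 8.2 / 8.8 | 20 points | 0.12 | 32% | 56% |
| 8.0 / 9.0 | 10 points | 0.11 | 25% | 45% |
| 8.0 / 9.0 | 20 points | 0.21 | 73% | 95% |
| 7.8 / 9.2 | 10 points | 0.16 | 48% | 77% |
| 7.8 / 9.2 | 20 points | 0.31 | 97% | nearly 100% |

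The comparator is about 2.5%, not 5%, because the rule needs a negative slope.

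**Step 3: check by drawing individual cases.** The fixed SD of 1.25 is too small for the widest gap, where the mixture SD is √(1.2² + 0.7²) = 1.39. Simulating individual cases (4,000 runs per cell) gives 10% to 91% at 200 per quarter and 17% to 99.5% at 400 over the same grid, and 2.4% to 2.9% with no shift.

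**Step 4: the reverse direction.** This was simulated at 257, 514 and 770 cases per quarter (5%, 10% and 15% of 5,136). With a gap of 0.8 g/dL, a true fall of 0.24 g/dL in both groups and an opposing 30-point shift, the slope is significantly negative in about 1.4% of runs, against 88% to 99.9% with no shift. Masking is only partial with a gap of 0.4, a true fall of 0.20 and an opposing 20-point shift: 35% to 72% detected.

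**Step 5: same test with fixed weights.** Replacing the crude median by a 50:50 average of the two group medians gives a significant negative slope in 1.4% to 3.6% of runs when neither group changes. It detects the 0.24 g/dL fall that the 30-point shift masks in 90% to 100% of runs.

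The Joinpoint step was not simulated. All percentages are for the slope test, not for the full declaration of Hypothesis 1.

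**The case against.** The strongest reply is that the plan already contains the remedy. Site-by-site trends are free of between-site mix, so a pooled fall with flat site slopes would be visible. The Secondary Outcome 4 model asks nearly the same question with adjustment. The study also calls itself descriptive, and a crude median is a fair description of what was measured in the population. Finally, sites must have data throughout the period, which limits entry and exit.

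Much of this stands. A reader might infer that the plan has no protection against mix effects, or that its conclusion will be an artefact. The documents support neither: the safeguards exist, and nothing shows that the mix drifts. A reader might also cite a site that cuts transfusions and so loses weight in later medians as an artefact without any change in practice. That example is weak, because such a site may well have changed practice. The cleaner routes are differential volume, specialty mix and hemoglobin testing.

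Three things do not stand. First, the institution-level analysis leaves specialty mix within a site untouched, and the gate can be read as stopping it when the pooled slope is null. Second, the Secondary Outcome 4 model has no say in the verdict. Third, the descriptive defence fails once a true-or-false ruling about practice is attached to the crude slope.

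**Conclusion.** The point holds as a flaw in the decision rule. Both the gate and the Hypothesis 1 verdict rest on an unadjusted pooled slope, for both primary outcomes, and no planned analysis can overrule it. The possible effect runs from minor (0.06 g/dL, 11% at 200 cases per quarter) to decisive (0.31 g/dL, 97%). Where the study would fall in that range cannot be told from the protocol, because the group gap, the mix drift, the SD and the number of usable transfused cases are all assumed. The top of the range should not be quoted as the expected false-positive rate. The change should be made, since it protects the primary conclusion at little cost.

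**What to change.** Reword the Primary Outcome 1 section, and through it Primary Outcome 2, so that both the gate and the Hypothesis 1 verdict use a site- and specialty-adjusted trend.

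- **Like-for-like option.** Apply the planned slope and Joinpoint steps to quarterly medians standardised to the whole-period site-by-specialty mix. With 8 × 10 = 80 cells and 200 to 400 cases per quarter, cells would average 2.5 to 5 cases, so state in advance how sparse cells are merged.
- **Model option.** Fit a case-level model on quarter with specialty and institution effects: pre-transfusion hemoglobin in transfused cases for Primary Outcome 1, nadir hemoglobin in non-transfused cases for Primary Outcome 2. Add site-specific slopes to address Hypothesis 4, since a common slope cannot show whether trends differ by site.

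In either case, keep the crude median as the descriptive plot, run the institution-level analysis whatever the pooled slope shows, and report any disagreement between the crude and adjusted results.

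The cost is protocol wording and one further analysis on variables already planned for extraction. The adjusted slope may be less precise, and the model option estimates means, not medians.
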